12.3 Appendix 3: Corneal Fluorescein Staining (CFS), Modified NEI Scale

The Investigator should use sufficient unpreserved saline solution (study stock) to wet the entire area of fluorescein impregnation on a 1.0 mg strip. If the strip becomes too saturated, discard and begin again with a new strip. Within 15 seconds of wetting the strip, taking care not to touch the strip to the eye, instill the fluorescein sodium in the inferior cul-de-sac. Instruct the subject to blink several times to distribute the fluorescein staining.

The Investigator should wait approximately 2 minutes after instillation of fluorescein before evaluating staining. A Wratten #12 yellow filter will be used to enhance the ability to grade fluorescein staining.

[figure not shown]
The cornea is divided into 5 sectors (central, superior, inferior, nasal, and temporal), each of which is scored on a scale of 0–4 in increasing increments of 0.5. Grade each of the 5 sectors of the cornea (central, superior, inferior, nasal, and temporal) in each eye. Total score (0-20) is obtained by summing the 5 sections of the cornea.

The grading results for each area, as well as the total score obtained from the scoring of the cornea, are to be recorded in the eCRF. Whenever possible, the same Investigator should perform the grading per subject.

Section 1 = Central, 2 = Superior, 3= Temporal, 4 = Nasal, 5= Inferior

[figure not shown]
OD: *Oculus dexter* (right eye)

OS: *Oculus sinister* (left eye)

[figure not shown]

Grade	Punctate Stain Spots
0	0 spots
0.5	1-7 spots
1.0	8-15 spots
1.5	16-22 spots
2.0	23-30 spots
2.5	31-37 spots
3.0	≥38 spots or too numerous to count (TNTC), must be <½ area, may be confluent but not coalescent
3.5	≥38 spots or TNTC, must be >½ area, may be confluent but not coalescent
4.0	≥38 spots or TNTC, must have coalescent area

12.4 Appendix 4:

[figure not shown]

12.5 Appendix 5:

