9.5.1.3. Efficacy Assessments

9.5.1.3.1. Primary Efficacy Assessment(s)

Corneal staining will be assessed at each in-clinic visit. The modified National Eye Institute (mNEI) scale defines 5 regions (central, superior, temporal, nasal, and inferior) of the eye and assigns a score of 0-4 to each region in increments of 0.5 to assess the severity of corneal staining. The sum of the 5 regions provides the total score.

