9.5.3. Primary Efficacy Variable(s)

Two primary ocular efficacy endpoints (one sign and one symptom) will be tested sequentially:

- Mean change from baseline (CFB) in total corneal fluorescein staining (tCFS; modified National Eye Institute [mNEI] scale, 0-20)

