9.7.1.5.1. Primary Efficacy Analysis

Primary Estimands: The primary estimands are the treatment differences between SY-201 Ophthalmic Solution arms and vehicle for mean CFB to Day 60 in tCFS using study eyes and mean CFB to Day 60 in eye [REDACTED] using the FAS.

Target Population: Subjects with DED who meet the study entry criteria.

Endpoints: Change from baseline at Day 60 for tCFS using study eyes and change from baseline at Day 60 for eye dryness score.

Treatment Condition(s): Treatment condition is based on the randomized treatment group.

Population-level Summaries: The difference in the mean CFB to Day 60 in tCFS using study eyes and the difference in mean CFB to Day 60 in eye dryness score and their p-values and corresponding 95% confidence intervals.

The proposed procedures to handle missing data and intercurrent events are as follows:

- Discontinuation of study therapy with continued participation in the study
 - Treatment Policy – no imputation; use observed data
- Receipt of rescue therapy
 - Treatment Policy – no imputation; use observed data
- Missing data with or without withdrawal, regardless of reason
 - Hypothetical approach – missing data will be accounted for assuming missing at random (MAR) using mixed-model repeated measures (MMRM).

Mean CFB in tCFS will be analyzed using a MMRM model. The model will include the baseline measurement, treatment, time, and treatment by time interaction as fixed effects, with a random effect for site. An unstructured covariance among repeated measurements is assumed. A similar model for the subject-level mean CFB in eye dryness score will be used.

Sample repeated measures model code:

```
PROC MIXED DATA=indata;
  CLASS subject center visit treatment(REF='Vehicle');
  MODEL change = baseline_value visit treatment visit*treatment / Solution DDFM=KR;
  REPEAT visit / SUBJECT=subject TYPE=UN;
```

```
RANDOM center;
LSMEANS treatment*visit / slice = visit DIFF CL;
RUN;
```

If the model fails to converge using this covariance structure, spatial power or compound symmetry will be implemented in this order.

Sensitivity analyses of the primary endpoints will be performed utilizing control-based pattern imputation, last observation carried forward (LOCF), and baseline observation carried forward (BOCF).

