Control-based pattern imputation would be performed using code similar to the below. The first call is to ensure a monotone missing data pattern. The second call is to perform the control-based pattern imputation.

```
PROC MI DATA=indata SEED= OUT=monotone MINIMUM=0 0 0 0 0 MAXIMUM=4 4 4 4 4 ROUND=0.5
NIMPUTE=25;
  MCMC IMPUTE = MONOTONE;
  VAR value_V2 value_V3 value_V4 value_V5 value_V6;
RUN;

PROC MI DATA=monotone SEED= OUT= MINIMUM=. 0 0 0 0 0 MAXIMUM=. 4 4 4 4 4 ROUND=0.5
NIMPUTE=1;
  by _imputation_;
  CLASS treatment;
  VAR value_V2 value_V3 value_V4 value_V5 value_V6;
  MONOTONE reg(/details);
  MNAR model(value_V3 value_V4 value_V5 value_V6 / modelobs= (treatment = 'vehicle'));
RUN;
```

Comparisons among individual arms will be obtained from the lsmeans statement. Comparisons between the combined SY-201 arm and Vehicle (least-squares means, treatment differences, 95% confidence intervals, and p-values) will be obtained using estimate statements. Assume treatments are ordered:

1. SY-201 2.0%;
2. SY-201 1.0%;
3. SY-201 0.5%;
4. Vehicle.

And visits 3, 4, 5, and 6 are ordered numerically. Let $n_{2.0\%}$, $n_{1.0\%}$, and $n_{0.5\%}$ be the total number of subjects for the appropriate arms in the respective analysis set (FAS or Per Protocol). Define

$$p_{2.0} = \frac{n_{2.0\%}}{n_{2.0\%} + n_{1.0\%} + n_{0.5\%}} \text{ with } p_{1.0} \text{ and } p_{0.5} \text{ defined similarly.}$$

To generate the estimates for the combined SY-201 for Visit 3, see the below code for an example for Visit 3.

```
estimate 'SY-201 Average V3'
  intercept      1
  baseline       <<overall average at baseline for all subjects>>
  visit          1 0 0 0
  treatment      p2.0 p1.0 p0.5 0
```

```
visit*treatment p2.0 p1.0 p0.5 0 0 0 0 0  
0 0 0 0 0 0 0 0;  
  
estimate 'SY-201 Average minus Vehicle V3'  
treatment p2.0 p1.0 p0.5 -1  
visit*treatment p2.0 p1.0 p0.5 -1 0 0 0 0  
0 0 0 0 0 0 0 0;
```

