9.7.2. Determination of Sample Size

For mean change from baseline to Day 60 in tCFS, a sample size of 45 SY-201-treated subjects versus 45 vehicle-treated subjects will have 87.9% power to detect an effect size of 2.0 units with a standard deviation of 3.0 for an unpaired t-test with a 2-sided alpha = 0.05. For mean change from baseline to Day 60 in dry eye symptom , a sample size of 45 SY-201-treated subjects versus 45 vehicle-treated subjects will have 83.5% power to detect an effect size of 1.5 units with a standard deviation of 2.4 for an unpaired t-test with a 2-sided alpha = 0.05.

Fifty (50) subjects per treatment arm, for a total 200 subjects, will be enrolled to allow for some dropout of subjects.

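### The sample code for the control-based imputation limits imputed values to 0–4, the range of one corneal region, although tCFS runs from 0 to 20

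*SAP*

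**What the plan says.** SAP 9.7.1.5.1 states: "Sensitivity analyses of the primary endpoints will be performed utilizing control-based pattern imputation", alongside LOCF and BOCF. The method is specified only by sample code, introduced with "Control-based pattern imputation would be performed using code similar to the below". The first PROC MI call, which makes the missing pattern monotone, carries "MINIMUM=0 0 0 0 0 MAXIMUM=4 4 4 4 4 ROUND=0.5" and the list "VAR value_V2 value_V3 value_V4 value_V5 value_V6": five visits, one value per visit. The second call does the control-based step. Its bound lists open with a missing-value dot followed by five zeros (minimum) and five fours (maximum), so there are six entries for the same five variables.

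On the scale, SAP 9.5.1.3.1 "assigns a score of 0-4 to each region in increments of 0.5" and makes the sum of the five regions the total. Protocol Appendix 3 agrees: "Total score (0-20) is obtained by summing the 5 sections of the cornea". SAP 9.5.3 defines the primary sign endpoint on the "modified National Eye Institute [mNEI] scale, 0-20".

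**The concern.** The bounds and the rounding match one region exactly, but the variables are visits, no region variable appears, and there is no summing step. Either the upper bound is wrong for tCFS, or a step that imputes region by region and then adds up has been left out.

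If the code is applied to the total, every imputed post-baseline tCFS value lies between 0 and 4, and a dropout who entered with more than 4 points must appear to improve. Control-based imputation is meant to make active-arm dropouts look like vehicle subjects and so test the missing-at-random assumption behind the primary MMRM. A cap that turns dropout into improvement can undo that test. LOCF and BOCF are the other two sensitivity analyses, so this is the only reference-based one.

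**Working it through.** **Inputs from the documents.** Region maximum 4 and five regions (SAP 9.5.1.3.1). Design effect 2.0, SD of change 3.0, and 45 evaluable of 50 enrolled per arm (SAP 9.7.2). The last implies 5/50 = 10% missing overall; no rate is stated.

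**Assumed, because the available text does not give them.** Baseline mean tCFS of 5, 6, 8 or 10; mean vehicle change of −1; dropout by arm.

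**The plan's own figure.** With 45 per arm, the noncentrality is 2.0 / (3.0 × √(2/45)) = 3.16 on 88 degrees of freedom. Power is 87.85%, against the stated 87.9%, so it reproduces. It does not depend on the imputation bounds.

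**1. Range.** The largest total is 5 × 4 = 20. The code allows 4, so (20 − 4)/20 = 80% of the scale is closed to imputed values.

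**2. One subject.** With baseline B, the forced improvement is at least max(0, B − 4): 0 at baseline 4 or below, 1 at 5, 2 at 6 (the whole design effect), 4 at 8, and 6 at 10.

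**3. Mean imputed Day 60 value.** Take draws from a normal with mean m = B − 1 and SD s = 3.0, restricted to [a, b]. The mean is m + s × [φ((a−m)/s) − φ((b−m)/s)] / [Φ((b−m)/s) − Φ((a−m)/s)]. The shift d is computed before rounding.

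| Baseline | m | Mean, 0–20 | Mean, 0–4 | d |
|---|---|---|---|---|
| 6 | 5 | 5.31 | 2.41 | −2.91 |
| 8 | 7 | 7.08 | 2.65 | −4.43 |
| 10 | 9 | 9.01 | 2.86 | −6.15 |

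**4. Arm difference.** The shift is approximately (missing share on active − missing share on vehicle) × d, for baselines 6 / 8 / 10:
- 10% and 10%: 0 × d = 0.
- 12% and 8%: 0.04 × d = −0.12 / −0.18 / −0.25.
- 20% and 10%: 0.10 × d = −0.29 / −0.44 / −0.62.
- 10% and 20%: the same sizes with a plus sign.

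**5. Simulation.** Two arms of 50, 2,000 replicates, 25 imputations, baseline SD 2.5, baseline slope 0.7, values missing at random within arm. Missing Day 60 values in both arms are drawn from the vehicle regression, redrawn within the bounds, rounded to 0.5 and compared by ANCOVA. Entries are the difference under the 0–4 cap minus that under 0–20, with Monte Carlo standard error 0.010 or less.

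| Missing, active / vehicle | Baseline 5 | 6 | 8 | 10 |
|---|---|---|---|---|
| 10% / 10% | within 0.02 | within 0.02 | within 0.02 | within 0.02 |
| 12% / 8% | −0.09 | −0.12 | −0.18 | −0.25 |
| 20% / 10% | −0.23 | −0.30 | −0.45 | −0.63 |
| 10% / 20% | +0.23 | +0.30 | +0.45 | +0.62 |

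**6. What the reader of the result would see, at baseline 8.**

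| True effect | Missing, active / vehicle | Bounds 0–20 | Cap 0–4 |
|---|---|---|---|
| −2.0 | 20% / 10% | −1.54 | −1.98 |
| 0 | 20% / 10% | 0.00 | −0.46 |
| −2.0 | 10% / 20% | −1.74 | −1.30 |
| 0 | 10% / 20% | −0.03 | +0.42 |

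In the first row, the control-based method should shrink the effect to about −2.0 × (1 − 0.20) = −1.60; the floor at 0 accounts for the small further loss. Under the cap the shrinkage disappears.

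**The case against.** The code is offered as a pattern to adapt: its seed and output names are blank, so it cannot be run as printed. The bounds match the regional scale so exactly that it may have been written for regional scores, with the summing step left unstated. On that reading the defect is one missing sentence and none of the bias above arises. This stands as a possibility. But the SAP does not say it, the code is the only specification of the analysis, and bounds are what a programmer copies.

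The cap acts on imputed values only, so observed scores above 4 stay as recorded. Read in order, the dot in the second call falls on the baseline visit; it may instead stand for treatment, which is in the CLASS statement but not the variable list. Both points narrow the problem, but post-baseline visits remain limited to 4.

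The larger shifts need 20% missing in one arm, twice what the sample size implies, and balanced dropout produces almost none. They also assume that out-of-range draws are redrawn. Setting such draws to the cap instead gives −0.35 rather than −0.44 at baseline 8 with 20%/10%. The protocol also asks discontinuing subjects to complete the Visit 6 assessments, which may limit missing Day 60 data. All of this bears on size, not on whether the bounds are wrong for the total.

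**Conclusion.** The point holds: as written, the bounds do not fit the tCFS total, and the alternative that would justify them is not in the available text. The forced improvement per dropout follows directly from the scale. The shift in arm difference is conditional: near zero with equal dropout, about 0.1 to 0.25 points at 12%/8%, and about 0.2 to 0.6 at 20%/10%, over baseline means of 5 to 10. It favours whichever arm loses more subjects. These figures rest on the assumed baselines, vehicle change, baseline slope, arm-specific dropout and redrawing within bounds.

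The damage is confined to one of three sensitivity analyses. The primary MMRM, the six-step hierarchy, the power, LOCF and BOCF do not use this code. The symptom score's range is not visible, so whether 0–4 suits it cannot be judged. The specification should be corrected before unmasking; no confirmatory result depends on it.

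**What to change.** For the tCFS total, set the minimum to 0, the maximum to 20 and rounding to 0.5 at each bounded visit; a sum of half-point scores is still a multiple of 0.5. Alternatively, state that each of the five regions is imputed with 0–4 bounds and the completed regions are then summed. Give the symptom score its own call with its own range and rounding. In the second call, supply exactly one bound per listed variable (five for Visits 2 to 6) and make clear what, if anything, the dot refers to.

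The cost is a few lines of SAP code, with no extra data and no burden on subjects. Changed after unmasking, it would be a post hoc correction to a pre-specified analysis.

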9.7.1.5.2. Secondary Efficacy Analyses

9.7.1.5.3. Exploratory Efficacy Analysis

Not applicable.

9.7.1.6. Analysis of Safety

Safety will be evaluated by:

1. Adverse event (AE) monitoring
2. Safety labs (chemistry and hematology)
3. Best Corrected Visual Acuity (BCVA)
4. Slit lamp biomicroscopy and external eye exam
5. Intraocular pressure (IOP)
6. Dilated ophthalmoscopy
7. Drop comfort assessment

The Safety Analysis Set will be used for all safety analyses. All data will be summarized as observed, and no data imputation will be performed. No statistical treatment group comparisons

will be performed, unless otherwise specified. Analyses will be presented by study eye and non-study eye, if applicable.

9.7.1.6.1. Adverse Events

AEs are coded using MedDRA Version 25.0. Treatment-emergent adverse events (TEAE) are defined as events that start on or after the first dose administration of double-masked study medication up to and including the last dose of double-masked study medication plus 30 days. Pretreatment adverse events are events that begin prior to first dose administration of double-masked study medication. Ocular AEs are defined as those events for which an eye has been specified (OD, OS, or OU).

Ocular and non-ocular TEAEs will be summarized separately. Ocular TEAEs will be presented by study eye and non-study eye and overall (OU) if an event occurs in either eye.

In all summaries of TEAEs, percentages are calculated based on the number of subjects in each treatment group of the Safety Analysis Set.

Overall summaries of TEAEs by treatment will include:

- the number of TEAEs and serious TEAEs reported;
- the number and percentage of subjects who experienced any TEAE;
- the number and percentage of subjects who experienced any serious TEAE and the reason for seriousness;
- the number and percentage of subjects with any TEAE by worst severity and worst relationship.
- the number and percentage of subjects with any TEAEs leading to discontinuation of double-masked study drug;
- the number and percentage of subjects with any TEAEs leading to study termination.

Summaries of the frequency and percentage of subjects with TEAEs by SOC and preferred term by treatment group will include:

- All TEAEs by SOC and preferred term;
- All TEAEs by SOC, preferred term, and maximum severity;
- All TEAEs by SOC, preferred term, and maximum relationship.

System organ class (SOC) will be sorted alphabetically, and preferred term (PT) within each SOC will be sorted by overall descending order of frequency according to the following rules in order:

1. Descending frequency within SY-201, 2.0%;
2. Descending frequency within SY-201, 1.0%;
3. Descending frequency within SY-201, 0.5%;
4. Descending frequency within Vehicle;
5. PT in alphabetical order.

Subjects are counted only once for each SOC and PT. In summaries of maximum severity and maximum relationship, subjects with multiple occurrences of events will only be counted once at the maximum severity/relationship per SOC and PT.

Any treatment-emergent AEs that have a missing severity will be presented as severe in the summary table but will be presented with a missing severity in the data listing. Any treatment-emergent AEs that have a missing relationship will be presented as “Related” in the summary table but will be presented with a missing relationship in the data listing.

All AEs are displayed in listings. In addition, separate listings will be provided for:

- Subjects with any treatment-emergent adverse event leading to study drug discontinuation or study termination;
- Subjects with any serious adverse event (treatment-emergent or otherwise);
- Subject deaths.

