3.1 Overall Design of the Study

This is a phase 2, multi-center, double-masked, randomized, vehicle-controlled, dose-response, parallel-group study designed to evaluate the ocular and systemic safety and ocular efficacy of SY-201 Ophthalmic Solution over a 60-day treatment period in subjects with moderate to severe DED.

During the 14-day single-masked run-in period, approximately 200 subjects will instill vehicle as 1 drop BID in both eyes (OU). At Visit 2, subjects will be randomized in a 1:1:1:1 ratio to 4 treatment groups: Vehicle (n=50) and SY-201 Ophthalmic Solution 2.0% (n=50), 1.0% (n=50), and 0.5% (n=50). Double-masked IP will be instilled as 1 drop OU BID for 60 days.

The study will consist of 6 clinic visits: Visit 1 (-14 Days, Screening), Visit 2 (Day 1, Randomization), Visit 3 (Day 7 ± 2 days), Visit 4 (Day 14 ± 2 days), Visit 5 (Day 28 ± 2 days), and Visit 6 (Day 60 ± 3 days, End of Study/Early Termination). A study schematic follows ([Figure 1](#)).

Figure 1: Study Schematic

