5.1.2 Dosage and Administration

This study includes a run-in period in which 1 drop of single-masked vehicle will be administered OU BID over 14 days. Administration of the double-masked IP, also 1 drop OU BID, will occur over a 60-day treatment period. In both periods, administration is preferred in the morning and evening, with 8 to 12 hours between instillations.

At Visit 1 (Day -14), subjects will be assigned of single-masked run-in product vehicle and self-administer their first dose under the supervision of the site staff.

Subjects will be instructed to instill the run-in product as 1 drop into each eye. Subjects will then take home their 3 assigned kits (sufficient for up to 15 days) of run-in product for self-administration. Subjects will dose at home that evening.

The used and unused containing single-masked run-in must be returned to the site at Visit 2 (Day 1). Subjects should **not** dose run-in product the day of Visit 2.

At Visit 2, randomized subjects will be assigned 2 IP kits of double-masked IP (SY-201 Ophthalmic Solution 2.0%, 1.0%, or 0.5% or vehicle). The first dose of double-masked IP, taken from an assigned kit, will be self-administered in the clinic by the subject under the supervision of the site staff. Subjects will be instructed to instill the IP as 1 drop into each eye. Subjects will be queried on drop comfort and then take home their 2 assigned kits (sufficient for up to 10 days) of double-masked IP for self-administration. Subjects will dose at home that evening.

Subjects will return the used and unused double-masked IP at each subsequent visit (through Visit 6) and receive new kits of double-masked IP to take home at Visit 3 (2 kits, sufficient for up to 10 days), Visit 4 (4 kits, sufficient for up to 20 days), and Visit 5 (7 kits, sufficient for up to 35 days).

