8.2.1 Adverse Events (AEs) and Serious Adverse Events (SAEs)

Adverse events will be monitored throughout the study. Subjects will be encouraged to report any adverse findings during the study whether or not they are related to IP. These can be collected either in an unsolicited fashion without any prompting or in response to a general question such as: "Have you noticed anything different since you started the study; began the IP, etc.?"

All AEs will be captured on the appropriate case report form (CRF). Information to be collected at minimum includes event description, onset, assessment of severity, relationship to IP, and outcome.

The Investigator will record all AEs with start dates occurring any time after informed consent is obtained until 7 (for nonserious AEs) or 30 days (for SAEs) after the last day of study participation. At each study visit, the Investigator will inquire about the occurrence of AE/SAEs since the last visit. Events will be followed for outcome information until resolution or stabilization.

Any medical condition that is present at the time that the subject is screened will be considered baseline and not reported as an AE. However, if the subject's condition deteriorates at any time during the study, it will be recorded as an AE.

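### The SAP's treatment-emergent definition has no clause for run-in adverse events that worsen on double-masked treatment, so whether they are tabulated depends on how the site records them

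*SAP*

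**What the plan says.** SAP 9.7.1.6.1 classifies AEs by start date alone. TEAEs "are defined as events that start on or after the first dose administration of double-masked study medication", and the window runs "up to and including the last dose of double-masked study medication plus 30 days". The next sentence takes everything else on the early side: "Pretreatment adverse events are events that begin prior to first dose administration of double-masked study medication". Neither sentence mentions worsening. Every AE table in that section is a TEAE table: incidence, worst severity, worst relationship, serious events, and events leading to discontinuation of drug or study. No table of pretreatment events is planned. The separate listing of AEs leading to discontinuation is also limited to treatment-emergent events.

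The design gives such events time to arise. Protocol 5.1.2 states: "This study includes a run-in period in which 1 drop of single-masked vehicle will be administered OU BID over 14 days". Protocol 8.2.1 starts collection at consent: "The Investigator will record all AEs with start dates occurring any time after informed consent is obtained".

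On conditions that change, Protocol 8.2.1 says "Any medical condition that is present at the time that the subject is screened will be considered baseline and not reported as an AE" and continues "However, if the subject's condition deteriorates at any time during the study, it will be recorded as an AE". Protocol 8.2.1.1 and SAP 9.5.1.4.1 both define an AE broadly enough to cover an exacerbation as well as a new finding.

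**The concern.** A run-in AE that is still present at Visit 2 and becomes worse on double-masked drops is on-treatment safety information. Under the SAP it carries a start date before the first double-masked dose, so as a single record it is pretreatment whatever happens to it later. Its later grade, its relationship to the investigational product and any resulting withdrawal then enter no by-arm AE table.

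Ocular safety is part of the primary objective (Protocol 2.1), and the TEAE tables are what a reader will use to compare arms. If sites record worsening differently, the same clinical event is counted at one site and omitted at another.

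**Working it through.** The plan gives no figure on this point, so there is none to reproduce. The check is to follow one event through the rules and then show what size the issue could have.

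**1. The event.** Take an AE that starts during the vehicle run-in, is mild and ongoing at Visit 2, becomes severe after the first double-masked dose and leads to withdrawal. Protocol 8.2.1 requires it to be recorded, because it began after consent.

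**2. Its fate under the two possible recording practices.**

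| Output in SAP 9.7.1.6.1 | One record, run-in start date | New record dated at worsening |
|---|---|---|
| Class | Pretreatment | TEAE |
| Incidence by system organ class and preferred term | Absent | Counted |
| Maximum severity and relationship tables | Absent | Counted |
| TEAEs leading to discontinuation, table and listing | Absent | Counted |
| Serious TEAE count, if serious | Absent | Counted |
| Listing of all AEs | Shown | Shown |
| SAE listing, if serious | Shown | Shown |

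**3. Does any passage require the right-hand column?**
- The deterioration sentence in Protocol 8.2.1 directly follows the sentence on conditions present at screening and qualifies it. A run-in AE was not present at screening, so the sentence does not clearly reach it.
- The AE definition permits an exacerbation to be entered as an AE in its own right. It does not say that a grade change in an ongoing AE opens a new record.
- Protocol 8.2.1 has events followed until they resolve or stabilize, which fits a single continuing record equally well.
- The partial-date rule in SAP 9.7.1 can move an incomplete start date to the dosing date, and so turn a run-in event into a TEAE. It applies only where a query has not produced a date. It does nothing for an event with a full date.

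The right-hand column is therefore allowed but not required.

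**4. Comparison with the protocol.** Protocol 9.4.3.1 has AEs that lead to study discontinuation both listed and tabulated, with no treatment-emergent restriction. SAP 9.7.1.6.1 restricts both to TEAEs. SAP 9.8.2 names one change from the protocol (time to first artificial-tear use) and not this one.

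**5. Size, by assumption.** The documents give no AE rates. Assume that 2% to 10% of the 200 subjects have a run-in AE ongoing at the first double-masked dose, and that 10% to 30% of those AEs worsen:
- subjects with an ongoing run-in AE: 200 × 0.02 = 4 to 200 × 0.10 = 20
- subjects whose event worsens: 4 × 0.10 = 0.4 to 20 × 0.30 = 6
- spread evenly over four arms: 0.4 / 4 = 0.1 to 6 / 4 = 1.5 per arm
- weight of one subject in an arm of 50: 1 / 50 = 2 percentage points

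These are upper limits for the given rates, because any worsening that a site enters as a new AE is already counted.

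**The case against.** The strongest reply is that the documents already treat worsening as an AE. Both define an AE to include exacerbation, and the deterioration sentence in Protocol 8.2.1 is broad when read without its context. A site that follows the AE definition could enter the worsening with its own onset date, and it would then be a TEAE as the SAP stands. Detailed recording rules often sit in eCRF completion instructions or the Manual of Procedures, which are not among the documents. This stands to the extent that omission is not certain. It does not close the gap, because neither the protocol nor the SAP settles the practice for run-in AEs.

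A second reply is that other outputs keep part of the signal. Baseline is the last value before double-masked dosing (SAP 9.7.1), so the slit-lamp shift tables (SAP 9.7.1.6.4) and the changes in visual acuity and intraocular pressure (SAP 9.7.1.6.3 and 9.7.1.6.5) would show post-Visit 2 worsening of the measured signs by arm. All AEs are listed, and SAEs are listed whether treatment-emergent or not. This also stands. These outputs do not give by-arm rates of symptoms, of relatedness or of AE-related withdrawal.

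A reader might go further and infer that the rule understates SY-201 toxicity relative to vehicle, since three arms switch to active drug at Visit 2 and one does not. The documents do not support that as a finding. The rule is identical in all four arms and percentages use each arm's own denominator. That three quarters of subjects are in active arms only restates the 1:1:1:1 allocation. A differential loss would require that SY-201 worsens run-in events and that sites keep them on one record. Neither is shown.

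**Conclusion.** The concern holds as a gap in the definition. A run-in AE that worsens on double-masked treatment is left out of every TEAE table, and of the listing of TEAEs leading to discontinuation, unless the site happens to enter the worsening as a new AE. The SAP also narrows what Protocol 9.4.3.1 promises for events leading to discontinuation, without declaring the change.

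A reader might infer that such events always disappear from the TEAE tables. That is too strong, because the AE definition allows a new entry, and a new entry dated on treatment is counted.

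The number affected is unknown and probably small. The range of 0.4 to 6 subjects rests wholly on assumed rates and on single-record practice at all sites. In arms of 50, one or two subjects could still change a row for severe events or for withdrawals. The efficacy analyses, power and type I error control are untouched. The change should be made because a stated rule can leave on-treatment worsening out of the tables and the repair is cheap.

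**What to change.** In SAP 9.7.1.6.1, extend the TEAE definition to include events that start before the first double-masked dose and increase in severity or become serious on or after that dose, with the same end of window. Change the pretreatment definition to match: events that begin before that dose and neither increase in severity nor become serious within the window.

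State that each worsening is counted once. If the site opened a new record for it, count that record and not the original. Without this rule one worsening could be counted twice in the total number of TEAEs. Subject counts are already limited to one per system organ class and preferred term.

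Before finalizing, check that the eCRF shows whether severity changed after the first double-masked dose. The minimum data items in Protocol 8.2.1 include onset and severity but not the date of a change in severity. If the eCRF does not hold this, one completion instruction is needed.

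The extended definition still leaves out a run-in AE that leads to discontinuation without worsening. Either tabulate all AEs leading to discontinuation, as Protocol 9.4.3.1 does, or record the restriction in SAP 9.8.2.

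The cost is one or two SAP sentences for the definition, an entry in SAP 9.8.2 if the restriction is kept, and a small amount of programming. No visits, subjects or assessments are added.
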